**Data Analyses for treatment and outcomes (Aims 1 and 3):** The sample of up to 500 participants will be split between HIV+ and HIV- participants. The participants will not be assigned at random to Suboxone® or methadone. The assignments will be based on clinical evaluation, and participants with a longer history of addiction, or with higher numbers of previous treatments, or participants who may be at risk for interactions between methadone and antiretroviral medications, will be more likely to receive Suboxone®. The investigators anticipate having about 40-50% of the sample receiving one medication, and 60-50% receiving the other, so there should be adequate numbers for analyses in each treatment stratum.

The goal of the analyses for Aims 1) and 3) is to assess the influences of participant characteristics on treatment outcome, and to examine whether characteristics of good outcome differ across treatment and HIV groups. Thus, the analyses will regard treatment (SUB or METH) and HIV status (+ve or -ve) as strata. Participant characteristics, drawn from the baseline administrations of the Study Specific Questionnaire, ASI, RAB, and ICD-10 assessments, will be the explanatory variables of interest, while binary factors for treatment group and for HIV status will form four strata.

The outcomes of interest include: (1) the durations of time in treatment, and time to relapse to drug use, which will be addressed using Cox proportional hazards models and its extensions; (2) measures of psychopathology and drug or sex risk behaviors, drawn from the ASI and the RAB at the 6 and 12 month points, which will be analyzed using linear or nonlinear (e.g. logistic or ordinal) mixed effects models; (3) self-reported drug use drawn from the ASI, and monthly UDS tests, which will also be analyzed using linear or nonlinear mixed effects models; (4) overall incidence of HIV among those participants negative for HIV at baseline, which will be analyzed using a logistic regression model.

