The analyses will follow the same overall analytic strategy for each set of models. First, the participant characteristics will be examined separately. For a given characteristic, the analyses will first test for heterogeneity (interaction) between the characteristic and the stratifying variables of treatment and HIV status. Two types of heterogeneity are possible: the characteristic could have effects that differ across some combination of the treatment and HIV groups (three-way interaction) or its effects may be independent of one variable but differ across levels of the other (two-way interaction). In either of these cases, stratum-specific estimates of the effects will be reported. If no heterogeneity is detected, the adjusted (pooled) estimates of effect will be reported. In each case, the estimates on an appropriate scale (e.g., odds ratios, or regression coefficients associated with interpretable changes in the level of the participant characteristic), together with appropriate confidence intervals will be reported. Once the univariate effects of the different characteristics will be assessed, multivariate models containing what appear to be the important characteristics will be performed, and these models will be implemented and reported in the same way as for the univariate models.

**Data Analyses for Economic Outcomes (Aim 4):** Standard cost-effectiveness and cost-utility analyses will compare costs and benefits of the two approaches (Gold et al., 1996; Haddix et al., 2003). The analyses will be carried out from a societal perspective which means that all costs and benefits, regardless of who pays or incurs them, will be included.

Benefits may be considered as reductions in sex risk behaviors (e.g., condom use and decreased number of partners) and less risky drug-use practices (e.g., decreased needle sharing and works sharing) during follow-up. In addition, a measure of the quality-adjusted life-years (QALYs) of sex partners saved by the intervention versus the standard of care will be estimated. Benefits will be compared to the direct and indirect costs (i.e., lost productivity) of the intervention and standard of care procedures. Relevant costs include time for the administration of the HIV counseling and testing, HIV test kits, completion of intervention questionnaires, time of staff to collect blood and follow-up assessment data and the time of participants to complete the follow-up assessments.

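### HIV incidence falls under the general interaction sequence with no exception: the HIV-status terms cannot be estimated there, and with few seroconversions ordinary logistic regression may report a zero or infinite odds ratio

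*Combined protocol and SAP*

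**What the plan says.** All of this is in the Combined protocol and SAP, Analysis Plan, under the data analyses for Aims 1 and 3.

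- The fourth outcome of interest is "overall incidence of HIV among those participants negative for HIV at baseline, which will be analyzed using a logistic regression model".
- Medication and HIV status are the stratifying variables for these analyses: "binary factors for treatment group and for HIV status will form four strata".
- The sequence is general: "The analyses will follow the same overall analytic strategy for each set of models". For each characteristic, "the analyses will first test for heterogeneity (interaction) between the characteristic and the stratifying variables of treatment and HIV status", and a three-way interaction is named as one possible finding.
- Reporting follows from the test. If heterogeneity is found, "In either of these cases, stratum-specific estimates of the effects will be reported". If not, "If no heterogeneity is detected, the adjusted (pooled) estimates of effect will be reported".
- Multivariate models come last, and "these models will be implemented and reported in the same way as for the univariate models".

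The plan does not name the heterogeneity test or its significance level. It gives no expected number of seroconversions, no minimum event count and no method for sparse events. Its statement that numbers will be adequate in each treatment stratum rests on the medication split, "about 40-50% of the sample receiving one medication, and 60-50% receiving the other", which counts participants and not events.

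**The concern.** There are two separate problems.

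The first is structural. The incidence analysis contains only participants who were HIV-negative at baseline. HIV status takes a single value there, so neither its interaction with a characteristic nor the three-way interaction exists. The plan prescribes both.

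The second matters more. How much a logistic model can support depends on the number of events, and one year of follow-up in about 300 people may yield only a handful of infections. If every infection falls in one level of a binary characteristic, the pooled maximum-likelihood odds ratio is zero or infinite. If heterogeneity is declared and one treatment-by-characteristic cell has no events, a stratum-specific odds ratio is zero, infinite or undefined. The plan has no rule for either case, so the handling would be chosen after the data are seen.

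The Innovation section names prevention of infection among HIV-negative entrants as one of the project's two prevention strategies, and this is the only planned analysis of observed new infections. As written, it commits to odds ratios for predictors but not to an incidence rate with a confidence interval.

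**Working it through.** **No plan figure to reproduce.** The documents give no incidence rate, event count or power calculation for this outcome.

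**Inputs from the documents.** Up to 500 participants; about 40% HIV-positive (Design), so 500 × 0.60 = 300 HIV-negative. Medication split 40/60 (Analysis Plan), so 120 and 180. Retesting at 6 and 12 months (HIV Testing), so about one year at risk. Follow-up above 90% at 12 months (Assessments).

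**Assumptions.** Incidence 1, 2, 3 or 5 per 100 person-years; the highest is included because the Background calls transmission from needle sharing high. Binary characteristic with prevalence 50% to 20%; no true effect; all 300 retested.

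**Structural check.** In an HIV-negative sample, a design matrix with an intercept, the characteristic, HIV status and their product has rank 2, not 4. The two HIV columns are zero for everyone.

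**Pooled estimate alone.** With n participants, prevalence p and event probability q, the chance that at least one level has no events is

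(1−q)^(np) + (1−q)^(n(1−p)) − (1−q)^n.

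At q = 0.02, n = 300:

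- p = 0.5: 2 × 0.98^150 − 0.98^300 = 2 × 0.0483 − 0.0023 = 9.4%.
- p = 0.2: 0.98^60 + 0.98^240 − 0.98^300 = 0.2976 + 0.0078 − 0.0023 = 30.3%.

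**Full sequence with a 5% likelihood-ratio test.** All event counts in the four treatment-by-characteristic cells were enumerated as independent binomials, and the no-interaction model was fitted to each table. A result counts as unusable if the test is significant and any cell is empty, or if it is not significant and one level has no events.

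| Rate per 100 person-years | Expected events (300 × rate) | Pooled alone, p = 50% to 20% | With 5% likelihood-ratio test |
|---|---|---|---|
| 1 | 3 | 39-59% | 47-64% |
| 2 | 6 | 9-30% | 19-36% |
| 3 | 9 | 2-16% | 10-22% |
| 5 | 15 | 0.1-5% | 4.5-10% |

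At 2 per 100 the second column of percentages splits as 9.4 + 9.5 = 18.9% (p = 0.5) and 30.3 + 5.6 = 35.9% (p = 0.2). The second term is the chance that the test is significant with an empty cell. A Wald test almost never rejects at 1 to 3 per 100, so it leaves the pooled-alone figures.

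These counts include samples with no seroconversion at all, where no regression would be run. That chance is 0.99^300 = 4.9% at 1 per 100 and 0.2% at 2 per 100. Without such samples, the first row becomes about 34-54% and 42-59%.

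**Sensitivity at 2 per 100.**

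- 270 retested: the pooled formula gives 2 × 0.98^135 − 0.98^270 = 12.7% at p = 0.5 and 0.98^54 + 0.98^216 − 0.98^270 = 34.4% at p = 0.2.
- The Background's other HIV prevalences, 30% and 51.8%, give 350 and 241 HIV-negative participants, and 15-30% and 25-44% with the likelihood-ratio test.
- One continuous, normally distributed score under the same test: 0.9% (4,000 simulated samples).

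**Multivariate step.** Treatment, two characteristics and two treatment interactions make five terms. With 3, 6, 9 and 15 events that is 0.6, 1.2, 1.8 and 3.0 events per term.

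**The case against.** The strongest reply is that any single percentage belongs to the reviewer's assumptions and not to the plan. The plan names no test and the documents give no incidence. At 50% prevalence and 2 per 100, half of the 19% comes from assuming a likelihood-ratio test. At 5 per 100 the problem is small. This stands, and it is why the result is given as a range with its conditions.

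Second, any analyst would drop a constant HIV term, and the word overall in the outcome's definition might suggest a pooled analysis. The first part is true, so the structural point changes no result. The second is not written: the sequence covers every set of models.

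Third, an infinite odds ratio is obvious on sight, a statistician supervises, and the plan asks for appropriate scales and confidence intervals. That leaves room for exact or penalised methods, but it is not a rule, and the model named is plain logistic regression.

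Fourth, ASI and RAB results are often used as scores, which are little affected. The RAB item on having injected at all is also constant at baseline, because eligibility requires injection in the past 30 days and the RAB looks back six months. The exposed variables are mainly single categorical items such as gender, marital status, employment and needle sharing.

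A reader might infer more: that the study's main results are compromised, or that the interaction and multivariate steps should be deleted for this outcome. The documents support neither. HIV incidence appears in neither outcome list, and the project disclaims any comparison of the two medications. The plan's stated goal is to learn whether predictors differ across groups, so deleting those steps whatever the event count would go beyond the defect.

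**Conclusion.** The point holds, with limited consequence. That the HIV-status and three-way interactions cannot be estimated follows from the text and needs no assumption. The sparse-event problem is conditional. At 2 per 100 person-years, with 300 HIV-negative participants all retested, prevalence 50% to 20% and no true effect, the chance of an unusable odds ratio for one binary characteristic is about 9-30% from the pooled estimate alone and 19-36% with a 5% likelihood-ratio test. It is larger at 1 per 100 and falls to about 0.1-5% and 4.5-10% at 5 per 100.

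It would be wrong to read 19-36% as a property of the plan. It would also be wrong to treat 5 per 100 as a rate at which a multivariate model becomes safe, since that still gives only 3.0 events per term in the five-term model. Primary and secondary outcomes are unaffected.

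**What to change.** In the Analysis Plan for Aims 1 and 3:

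1. State that for HIV incidence only the treatment stratum applies.
2. Report seroconversions per 100 person-years with an exact Poisson 95% interval, overall and descriptively by medication. State in advance how person-time is counted between tests, and report how many were never retested. The interval is usable at any count. On 285 person-years (300 people, 10% lost on average halfway: 270 + 15), 0 events gives 0 to 1.29, 6 events 0.77 to 4.58 and 14 events 2.69 to 8.24 per 100.
3. Fit any predictor model by Firth-penalised or exact logistic regression in place of ordinary logistic regression, labelled exploratory. For 0/150 against 6/150, the Firth odds ratio is (0.5/150.5)/(6.5/144.5) = 0.07, where maximum likelihood gives 0.
4. Run the treatment-interaction and multivariate steps only if a pre-stated minimum number of seroconversions is reached.

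The cost is a few sentences; the HIV tests are already scheduled. The downsides are that penalised estimates are shrunk toward no effect, and that the multivariate step may not be run if events are few.

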## **Design**

This is an open-label follow-up study. The project proposes to enroll up to 500 opiate dependent individuals entering Medication Assisted Treatment (Methadone or buprenorphine/naloxone) at Go Vap Clinic, HCMC, Vietnam. All participants who appear to meet inclusion criteria and who express interest in drug treatment will be invited to be screened for participation in the research. The investigators expect that around 40% of them will be also HIV-positive and so will receive appropriate treatment. All participants will receive BDRC sessions (weekly for 12 weeks, monthly thereafter until week 52).

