**Assessments:** As described below, the assessment interviews for each participant will include: 1) the locator questionnaire; 2) a brief study specific questionnaire that will be used to capture relevant socio-demographic data, health status, medical and drug treatment history and living situation and family relationships; 3) the Addiction Severity Index (ASI), 4) the Risk Assessment Battery (RAB); 5) the ICD-10; and, 6) the WHO Quality of Life (QOL) scale. At monthly intervals, urine specimens will be collected for testing evidence of continued drug use and blood will be collected for HIV testing at baseline, 6 and 12 months. Research staff will also collect data from the program records regarding clinic attendance and methadone dosage and will keep a log of all counseling sessions attended, their duration and copies of all session content checklists.

All assessments will be completed by trained research staff (not clinicians or counselors) at baseline, and again at 6-, and 12-month post-enrollment. Importantly, assessments will be completed on those who remain in treatment as well as those who leave the program. The investigators anticipate follow-up rates exceeding 90% after 12 months.

**Locator Data Collection:** A basic philosophy of the research approach to be implemented is that follow-up begins at recruitment and enrollment. Thus, a detailed contact sheet (Locator Form) will be completed for all subjects as part of the baseline assessment. This locator form will be updated at each subsequent assessment visit. Participants in the research will also be asked to call or visit the research office in the clinic whenever they have questions about assessment schedules or have updates to provide regarding changes in contact information. Participants will be asked to provide contact information on themselves and three additional people with whom they are most likely to stay in contact. They will also be asked about other

places where they might be able to be contacted in the future. This instrument will be modeled after the Locator form developed in Philadelphia and will be modified and translated by the investigators in Vietnam.

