WHO QOL-BREF: For assessing quality of life, the World Health Organization Quality of Life (WHOQOL)-BREF will be used. Assessments will be completed at baseline, month 3, 6, 9, and 12. The World Health Organization Quality of Life (WHOQOL) project was initiated in 1991 to develop an international cross-culturally comparable quality of life assessment instrument. It assesses the individual's perceptions in the context of their culture and value systems, and their personal goals, standards, and concerns. The WHOQOL instruments were

developed collaboratively in several centers worldwide and have been widely field-tested. The WHOQOL-BREF is a self-administered, standardized instrument used as a measure of health outcome and comprises 26 items, which measure the following broad domains: physical health, psychological health, social relationships, and environment. The WHOQOL-BREF is a shorter version of the original instrument that may be more convenient for use in large research studies or clinical trials. It has been used in international settings, including the WHO collaborative study of substitution treatment (Lawrinson et al, 2008).

Urine testing: Urine drug testing will be done using rapid test kits that test for opiates, amphetamines, methamphetamines, benzodiazepines, and cannabis. These will be purchased from an approved laboratory in Vietnam. These kits provide a rapid urine test that is done on site and produces a result within five minutes. In this study, urine testing will be done monthly, with collection days being randomly selected.

HIV Testing: At the baseline visit rapid HIV testing will be used to determine HIV status and need for care. All participants who are determined to be HIV positive (two rapid positives) will be referred directly to Go Vap HIV clinic for initial assessment. All participants who test negative will be scheduled for retesting at 6- and 12-month assessment points. The test kits to be used will be WHO tested and selected in conjunction with the HCMC MOH.

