**Study Retention:** A series of structured activities will be used to maximize completion of follow-up appointments. These activities are considered core principles in conducting longitudinal studies and have been shown successful in many different cultural settings. The investigators believe that with the intensive and structured efforts described below, the proposed project can achieve a 90% retention rate at 12 months. Most importantly, research staff will maintain accurate and timely follow-up contact information for all participants throughout the study. A basic philosophy of the work to be implemented is that follow-up begins when the initial relationship is established, and the data is collected at the time of recruitment and enrollment. Thus, a detailed locator interview will be completed for all subjects following completion of the informed consent at the time of enrollment. This will be updated at all subsequent contacts. All future appointments for research assessments will be scheduled on a calendar at the time of enrollment. A copy of this visit schedule will be given to the participant. Ten days prior to all scheduled assessment visit, calls reminding subjects about their scheduled assessment will be completed and a note will be left in the methadone dispensing area reminding the participant about the time and location of the assessment visit. Missed calls will be noted and attempts to contact the participant will continue until contact is achieved. For those who are not able to be contacted through the clinic or by phone, staff will visit contact locations collected from the participant at the time of enrollment and updated at their most recent contact. Reminder calls will also be made on the day before the scheduled appointment. Missed appointments will be responded to immediately. At the end of each day, the designated follow-up staff will attempt to contact all the subjects who missed their appointment that day. For those who unable to be reached by phone, a reminder letter will be sent within three days. Outreach by research staff will also be used to locate missing subjects. When unable to make contact after 5 days, research staff members will implement outreach procedures, including visiting the subject's home, contacts, and common "hangouts" reported by the subject at the time of their prior visit. Subjects who are reported to be incarcerated will have a note placed in their retention file and staff will periodically update the status of the participant through contact with the friend or family member who initially reported the incarceration.

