
### **Analysis Plan**

All data will be collected by research staff based at the Go Vap clinic. Trained staff will review all forms prior to the completion of the study visit to minimize problems associated with missing values and incorrect skip patterns. All assessments will be recorded on final version of the Case Reporting Forms (CRFs). CRFs will also be developed to capture the results of all biological assessments. All CRFs will be completed and stored using only participant identifying numbers and will not include names, addresses, or other data that could possibly be used to disclose the identity of the participant. All completed CRFs will be filed in locked cabinets by ID number. Consent forms, locator information, and other forms with personal identifiers will be securely stored separately. Research staff at the project site will be responsible for entering all data into the secure web-based data management system operated by the Data Management Unit of the University of Pennsylvania, Center for Studies of Addiction (CSA).

The data management and the quantitative analyses will be performed by the Center for Studies of Addiction data analyst, under the supervision of the PI and [name], the CSA Statistician. [name] will supervise the economic analyses. Prior to performing analyses, standard data screening and cleaning procedures will be applied (Tabachnik & Fidell 2001). These procedures will (1) screen the data for data-entry errors, (2) check for outliers, (3) assess the extent and pattern of missing data, and (4) check that appropriate assumptions of normality are met whenever necessary.

The planned analyses will be sharply focused on providing information able to inform the primary aims of the study.

- 1) *Establish a new integrated MAT treatment program within and HIV treatment setting in HCMC.* This aim will be fully documented by descriptive data focused on the numbers of patients treated by methadone and Suboxone. Data to summarize the duration of and response to treatment by patients in each of the four groupings—Methadone treated HIV-; Methadone treated and HIV+; Suboxone® treated and HIV-; and Suboxone® treated and HIV+ will be presented. The project's goal is not to compare treatment but to provide data to demonstrate that these treatments are producing results consistent with “clinical expectations” for these approaches and patient populations.

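### HIV incidence is assigned a logistic model with no follow-up time and no rule for participants without a 12-month test, so the estimate depends on an unstated coding

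*Combined protocol and SAP*

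**What the plan says.** The Analysis Plan (Data Analyses for treatment and outcomes, Aims 1 and 3) gives outcome (4) as "overall incidence of HIV among those participants negative for HIV at baseline, which will be analyzed using a logistic regression model". It states no time point, denominator, follow-up time or offset. Treatment duration and time to relapse, in the same list, get Cox models, and the repeated ASI, RAB and urine outcomes get mixed models.

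The testing schedule is the same for everyone at risk. Under HIV Testing, "All participants who test negative will be scheduled for retesting at 6- and 12-month assessment points", and under Assessments, "blood will be collected for HIV testing at baseline, 6 and 12 months".

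On completeness, the Assessments text says "The investigators anticipate follow-up rates exceeding 90% after 12 months", and Study Retention says "the proposed project can achieve a 90% retention rate at 12 months". People who stop treatment are still followed: "assessments will be completed on those who remain in treatment as well as those who leave the program".

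The only missing-data provision is a screening step to "assess the extent and pattern of missing data". No handling rule is given for this outcome.

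**The concern.** A single yes/no record per person has no natural place for someone who tests negative at 6 months and has no 12-month result. Three codings are open, and they lead to different places:

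- Carry the 6-month negative forward as uninfected for the year. Infections in months 6 to 12 are missed, so incidence is under-counted.
- Keep people positive at 6 months but drop 6-month negatives without a 12-month test. The denominator shrinks and the numerator does not, so incidence is over-counted.
- Analyse only people with a 12-month test. This is unbiased if loss is non-informative, but it discards completed 6-month intervals and any seroconversion seen in them.

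The outcome has some weight. The Innovation section names prevention of infection in HIV-negative participants as one of two strategies behind the project. The economic analysis names HIV transmissions prevented as a possible effect measure. A figure whose direction of error depends on an unwritten rule is hard to use there or to set beside a rate from another cohort.

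**Working it through.** **No plan figure to reproduce.** The documents give no expected HIV incidence, event count or power for this outcome.

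**Inputs from the documents.** "The project proposes to enroll up to 500 opiate dependent individuals" (Design), with about 40% expected to be HIV-positive (Design). At risk: 500 × (1 − 0.40) = 300. At 90% follow-up the share m without a 12-month test is 0.10, or 300 × 0.10 = 30 people.

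**Assumptions (not in the documents).** Half of those without a 12-month test have a 6-month test. Infections are rare and spread evenly over the year. In steps 1 and 2, loss is unrelated to infection risk.

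**Step 1: overall incidence.** Attenders at 12 months contribute all their infections (1 − m). Those tested only at 6 months contribute half of theirs (0.5m × 0.5). The never-retested contribute none. Captured share = (1 − m) + 0.25m = 1 − 0.75m = 0.925 at m = 0.10.

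| Coding | Captured share ÷ share in denominator | Relative error |
|---|---|---|
| All without a 12-month test counted negative | 0.925 / 1.00 = 0.925 | −7.5% |
| Never-retested excluded, 6-month negatives carried forward | 0.925 / 0.95 = 0.974 | −2.6% |
| 6-month positives kept, 6-month negatives dropped | 0.925 / 0.90 = 1.028 | +2.8% |
| 12-month attenders only | 0.90 / 0.90 = 1.000 | 0% |

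Range for the one-half assumption: if all 30 have a 6-month test, carrying forward gives about −5% and the drop rule about +5%. If none has, counting them negative gives −10%.

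**Step 2: a predictor with true odds ratio 1.** With equal 10% loss at both levels, the odds ratio is essentially unchanged under every coding. Now assume 5% versus 15% loss, which averages 10% in equal-sized groups. For a rare outcome the odds ratio is close to the ratio of the factors above.

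- All counted negative: (1 − 0.75 × 0.15) / (1 − 0.75 × 0.05) = 0.8875 / 0.9625 = 0.92.
- Never-retested excluded: (0.8875 / 0.925) / (0.9625 / 0.975) = 0.959 / 0.987 = 0.97.
- Drop rule: (0.8875 / 0.85) / (0.9625 / 0.95) = 1.044 / 1.013 = 1.03.

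At an assumed 70% follow-up (15% versus 45% loss), which is well below the protocol's expectation, the same formulas give 0.75, 0.89 and 1.15.

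**Step 3: sampling error.** At an assumed 5 infections per 100 there are 300 × 0.05 = 15 events. For a 50/50 predictor with no effect that is 7.5 of 150 in each group. The standard error of the log odds ratio is √[2 × (1/7.5 + 1/142.5)] = 0.53, so the 95% interval around 1 is about 0.35 to 2.8. At 3 per 100 it is about 0.27 to 3.8. The shifts in step 2 at 90% follow-up are small beside this.

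**Step 4: loss related to infection risk.** Suppose the 10% lost have three times the hazard of those retained, and only 12-month attenders are analysed. With 5 per 100 person-years in the retained, true incidence is 0.9 × 0.0488 + 0.1 × 0.1393 = 0.0578 against an estimate of 0.0488, an error of −16%. Across retained rates of 1 to 10 per 100 person-years the error is −15% to −17%. With twice the hazard it is −8% to −9%.

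**Step 5: what an interval-based analysis gives.** If all 30 have only the 6-month test, person-time is 270 × 1 + 30 × 0.5 = 285 person-years, ignoring the little time after infection. At 5 per 100 person-years about 14 events are expected, with an exact 95% interval of 2.69 to 8.24 per 100 person-years. The error from unequal follow-up in step 1 disappears. The error in step 4 is not removed.

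**The case against.** The best defence is that everyone at risk has the same 12-month schedule, so logistic regression on 12-month status is a standard analysis of one-year cumulative incidence. Restricted to 12-month attenders it is unbiased under non-informative loss, and equal loss leaves odds ratios alone. A pooled logistic model with one record per test interval would also fit the plan's wording. People who leave treatment are traced by locator data and outreach, so leaving the program is not the same as missing the test. At 90% follow-up the distortion is minor and few events limit this model far more. All of this stands.

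A reader might therefore infer either that nothing is wrong or, in the other direction, that unequal follow-up definitely biases both the incidence and its predictors. The documents support neither. The plan specifies no restriction to 12-month attenders and no interval records, so the defence rests on choices not written down. The stronger charge fails too: testing at two times is not a fault, bias is not certain, and predictor effects move only if loss differs by the predictor or is related to risk.

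Such loss is plausible but not shown. The background section on drug treatment as HIV prevention cites less injecting among patients who stay than among those who leave. Study Retention describes a file note and status updates for incarcerated participants and mentions no testing. Involvement with the criminal justice system is recorded in the Study Specific Questionnaire, which supplies candidate predictors.

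**Conclusion.** The point holds as a gap in specification with a better method readily available, at low to moderate severity. The plan names an incidence outcome, gives it a model without follow-up time, and does not say what happens to the roughly 10% who may lack the 12-month test.

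With non-informative loss and half of those people having a 6-month test, the error in overall incidence runs from −7.5% to +2.8% according to the coding, and is −2.6% if 6-month negatives are carried forward and only people with a retest are analysed. Under the assumed 5% versus 15% loss, a null predictor's odds ratio lies between about 0.92 and 1.03. That is too small, beside the sampling error, to make a characteristic look protective or harmful by itself. Larger distortions need follow-up well below the protocol's target or loss tied to infection risk, and both are assumptions. HIV incidence is in neither the primary nor the secondary outcome list, which also limits the weight of the point.

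**What to change.** In outcome (4) of the Analysis Plan:

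- Report seroconversions per 100 person-years with an exact confidence interval. Time runs to the last negative test, or to the midpoint of the interval containing the first positive test.
- Replace the single-record logistic model with an interval-based one: a discrete-time complementary log-log model with log interval length as offset, or pooled logistic regression with an interval term. A participant tested only at 6 months then contributes exactly that interval. The complementary log-log form also takes a 0-to-12-month interval when the 6-month test was missed; the pooled logistic form would need a separate interval category for it.
- Add a simple sensitivity analysis for informative loss, for example assigning untested intervals two or three times the observed hazard.

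The cost is a few sentences, with no new tests or data. Two limits remain. The rate needs a midpoint assumption, and bias from informative loss is not removed, only explored by the sensitivity analysis.
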